## 1. Introduction

### 1.1 Overview of the Problem

HIV infection among men who have sex with men (MSM) in Vietnam continues to rise, with prevalence in Ho Chi Minh City (HCMC) estimated at 17% and incidence among young MSM (YMSM) in Hanoi at 5.8%. Behavioral risks such as unprotected sex, multiple partners, and untreated STIs sustain high levels of circulating virus within MSM networks. Low HIV testing rates and poor engagement in care further exacerbate transmission. Meanwhile, widespread smartphone and internet use among Vietnamese MSM offers an opportunity for online testing innovations.

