## 2. Study design and methods of data collection

This study aims to evaluate the effectiveness of the HIV self-testing with online supervision (STOS) intervention, which includes the introduction of a HIV rapid diagnostic antibody/antigen-based self-testing conducted with the support of a trained counsellor via video conferencing, among young men who have sex with men (YMSM) aged 16–29 years.

The study employs a pilot randomized controlled trial (RCT) design with two groups: an intervention group (STOS) and a control group. The total sample size is 100 participants (50 per group). The follow-up period spans 12 months, with data collected at three time points: baseline, 6 months, and 12 months.

Data collection includes self-administered online questionnaires completed through the Qualtrics platform. For participants in the intervention group, the study involves the implementation of real-time online supervised HIV self-testing conducted by a trained counsellor through video conferencing.

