## 2.1 Procedures

### 2.1.1 Recruitment and Enrollment

Participant recruitment will be conducted over a one-year period, using a combination of online and offline outreach strategies to reach the target population of young men who have sex with men (YMSM) in Ho Chi Minh City.

For the online cross-sectional survey, recruitment will primarily be conducted through online platforms, including Google advertisements, Facebook, the CARMAH fan page, CARMAH networks, other MSM community networks, and youth networks in Ho Chi Minh City (such as university and high school students). To encourage participation, each respondent will receive a mobile top-up e-voucher valued at 50,000 VND (approximately 2 USD), delivered via SMS.

Individuals interested in participating will complete an online eligibility screening form. Those who meet the inclusion criteria will receive detailed study information and proceed with the initial electronic consent (e-consent). After completing the survey, if an individual is found to be HIV-positive, they will not be invited to participate in the pilot study.

For the pilot study, a total of 100 Vietnamese YMSM will be recruited and followed for 12 months. Participants will be randomly assigned into two groups of 50 each:

- The intervention group, which will receive the HIV self-testing with online supervision (STOS) intervention; and
- The control group, which will refer to the standard of care, consisting of a voucher for venue-based HIV testing.

The STOS program begins when a counsellor contacts eligible participants via the Zalo communication platform. After confirming eligibility, the counsellor obtains verbal informed consent and schedules an appointment for the HIV self-testing with online supervision (STOS) session.

Once the appointment is confirmed, HIV self-testing kits are delivered to participants through Be Delivery service. Before the testing session, participants receive a link to an instructional YouTube video developed by CARMAH and Mahidol University, which demonstrates the correct procedure for performing the HIV self-test.

During the scheduled session, the counsellor provides pre-test counselling and real-time supervision via video conferencing as participants perform the self-test. This process ensures proper use of the test kit, supports accurate interpretation of results, and maintains participant confidentiality throughout the HIV self-testing process.

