### 2.1.3 Retention and Engagement Strategies

To ensure sustained participation throughout the follow-up period, the research team will implement continuous engagement measures using multiple digital communication channels, including the Zalo application, SMS, telephone calls, and support from community peer leaders. Participants will be contacted regularly to receive project updates, appointment reminders, and encouragement to take part in each data-collection round. Ongoing assistance will also be provided to help maintain participants' motivation and consistency in completing questionnaires. For the STOS group, follow-up communication will additionally ensure that participants receive their self-testing kits. These combined strategies are expected to achieve follow-up retention rates exceeding 80% at each assessment point.

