#### 2.4.2 Primary and Secondary Outcome Analyses

To evaluate the effects of the STOS intervention, two groups will be compared: the STOS group, who receive an HIV self-testing kit and complete the online questionnaires, and the control group, who complete the questionnaires only. The primary outcomes are the rate of HIV testing uptake and the rate of new HIV infections during the study period. The secondary outcomes include changes in sexual behaviors, mental health, and other psychosocial indicators over time. To assess the effects of the intervention across time points, Generalized Estimating Equations (GEE) models will be applied, using a log link function for rate outcomes and an identity link function for continuous outcomes. The models will include variables for study arm (STOS vs. control), time (follow-up round), and their interaction term (arm  $\times$  time) to estimate longitudinal intervention effects. Robust standard errors will be used to account for within-subject correlation due to repeated measures. The results will be presented as Rate Ratios (RRs or Incidence Rate Ratios, IRRs) with 95% confidence intervals (CIs) and p-values to indicate the magnitude and statistical significance of the observed effects.

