#### 3.4 Secondary Outcomes

- **HIV incidence:**

Number of new HIV infections per 100 person-years, based on STOS testing results and self-reported data during follow-up.

- **Sexual risk behavior:**

Proportion of participants reporting condomless anal intercourse with male partners during the past 6 months, measured through self-reported survey data.

- **Health-related risk behaviors (mental health and substance use):**

Proportion of participants reporting mental health problems (e.g., depressive symptoms, suicidal risk) and frequency of substance use during the past 6 months, based on self-reported survey data.

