## 6.2 Primary and Secondary Outcome Analyses

Generalized Estimating Equations (GEE) with appropriate link functions (e.g., logit for binary outcomes, identity for continuous variables) will be applied to assess intervention effects

over time. Each model will include study arm, follow-up time, and an interaction term to estimate differential changes between groups. Robust standard errors will be used to account for correlations within individuals. Person-time will also be calculated, and rate ratios with 95% confidence intervals will be reported.

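### HIV incidence is modelled with an arm-by-round interaction that will often have no finite estimate and, when it has one, is not the intervention effect

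*Combined protocol and SAP*

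**What the plan says.** SAP 6.2, which covers primary and secondary outcomes together, prescribes GEE with robust standard errors and states: "Each model will include study arm, follow-up time, and an interaction term to estimate differential changes between groups". Protocol 2.4.2 matches it: "The models will include variables for study arm (STOS vs. control), time (follow-up round), and their interaction term". The protocol adds a log link for rate outcomes and reports rate ratios or incidence rate ratios. It describes the terms as estimating longitudinal intervention effects.

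HIV incidence is within scope under either document. Protocol 2.4.2 lists the rate of new infections as a primary outcome. SAP 3.4 lists it as a secondary outcome, defined as "Number of new HIV infections per 100 person-years, based on STOS testing results and self-reported data during follow-up".

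SAP 6.2 closes by saying that person-time will be calculated and rate ratios with 95% confidence intervals reported. It does not say whether these come from the GEE or from a separate pooled comparison. Neither document gives an expected number of infections, a method for sparse events or a fallback. SAP 7 allows alternative specifications, link functions or mixed models, but as options and not as a remedy for empty cells.

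**The concern.** One model form is applied to outcomes of very different frequency. Testing uptake may support an arm-by-round model in 100 men. New infections will number only a handful, and the model divides them among four cells. A log-link model with all three terms fits the four cells exactly, so a cell without infections drives a coefficient to infinity.

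The second difficulty does not depend on the incidence. Men found to be HIV-positive at the survey are not invited into the pilot (protocol 2.1.1), so incident infection has no baseline level. The interaction therefore compares the second half of follow-up with the first. It does not compare follow-up with baseline, as it would for a behaviour measured at all three visits.

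At stake is an outcome that the protocol calls primary. The planned model may give no usable interaction, or a numerical artefact with a small standard error, or a finite coefficient that is mistaken for the effect of STOS.

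**Working it through.** The documents state no expected event count, power or effect size for incidence, so there is no figure of theirs to reproduce.

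**Inputs**
- Incidence: protocol 1.1 gives "incidence among young MSM (YMSM) in Hanoi at 5.8" per cent. No person-time unit is stated; it is read here as 0.058 per person-year.
- Arms: "Participants will be randomly assigned into two groups of 50 each" (protocol 2.1.1).
- Rounds: "The follow-up period spans 12 months, with data collected at three time points: baseline, 6 months, and 12 months" (protocol 2). This gives two 6-month intervals and four arm-by-round cells, with round treated as a category.
- Retention: protocol 2.1.3 expects "follow-up retention rates exceeding 80% at each assessment point". Used here: 100% and 80%.
- Rate ratio (RR): the documents give none. Used here: 1, and 0.5 as an assumption.

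**Formulas (Poisson)**
- Expected infections per cell: m = 50 × retention × 0.5 × 0.058 × RR, with RR = 1 for control.
- P(at least one of four cells empty) = 1 − (1 − e^−m_control)² × (1 − e^−m_STOS)².
- P(at least one arm has no infections over 12 months) = 1 − (1 − e^−2m_control) × (1 − e^−2m_STOS).

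First case: m = 50 × 1 × 0.5 × 0.058 = 1.45; e^−1.45 = 0.2346; 1 − 0.7654⁴ = 0.657.

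| RR | Retention | m control | m STOS | Any cell empty | Any arm empty |
|---|---|---|---|---|---|
| 1 | 100% | 1.45 | 1.45 | 65.7% | 10.7% |
| 1 | 80% | 1.16 | 1.16 | 77.8% | 18.7% |
| 0.5 (assumed) | 100% | 1.45 | 0.725 | 84.4% | 27.7% |
| 0.5 (assumed) | 80% | 1.16 | 0.58 | 90.9% | 38.1% |

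A binomial simulation in which infected men leave the risk set gave 66.8%, 78.8%, 84.9% and 91.3% for the empty-cell column.

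**Sensitivity to the incidence** (RR 1, full follow-up): at 3 per 100 person-years, m = 0.75 and the probability is 92%. At 8 per 100, m = 2.0 and it is 44%.

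**What an empty cell does.** A constructed data set with cell counts 2, 1, 1 and 0 was fitted by log-link GEE in Python statsmodels. The interaction coefficient was −21.0 with a robust standard error of 1.6. That is about 13 standard errors from zero (21.0/1.6) and carries no information. Models with arm only, or with arm and round, stayed finite. Stata was not tested.

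**What the interaction measures.** With rounds 0–6 and 6–12 months, exp(interaction) = RR(6–12) / RR(0–6). If STOS halves incidence throughout, this is 0.5/0.5 = 1.

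**Precision when nothing is empty.** With 1.45 infections in every cell, the interaction's standard error is √(4/1.45) = 1.66, so its 95% interval is about ×/÷ 26. The pooled ratio with 2.9 infections per arm has standard error √(2/2.9) = 0.83, or ×/÷ 5. With 2.32 versus 1.16 it is ×/÷ 9.

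**The case against.** A reader might infer that no planned rate ratio for incidence can be estimated. The documents do not support that. SAP 6.2 separately promises person-time rate ratios, and its wording can fairly be read as a comparison alongside the GEE. A pooled 12-month ratio fails only when a whole arm has no infections, in 11% to 38% of trials in the scenarios above. A single empty cell also leaves the other round's ratio finite. At least one round has infections in both arms in 83%, 72%, 63% and 51% of trials, in the order of the table. What stands against the plan is narrower: the interaction and the affected round's ratio are lost, and the SAP does not say how the person-time ratio is obtained.

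A reader might also take the whole range of 66% to 91% as following from the protocol's own figures. Only 66% to 78% does, given the assumed unit. The upper part also needs a halving that no section states. The incidence figure itself is for Hanoi, and the trial is in Ho Chi Minh City.

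Neither document says that the interaction alone will be reported as the effect. The model has an arm term, and the SAP's description of the interaction as differential change is accurate; the protocol's description is looser. Nor is GEE ruled out because a man can be infected only once: person-interval records with robust standard errors are a legitimate way to estimate a rate. If time entered as a linear term, one empty cell need not make the interaction infinite, but the protocol's reference to follow-up round points to categories.

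Finally, this is a pilot, the SAP makes incidence secondary, and no method will give it useful power. That is a fair argument on severity. It does not justify keeping a model that can return a meaningless coefficient.

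**Conclusion.** The concern holds for the interaction term and the round-specific rate ratios. Reading 5.8% as 5.8 per 100 person-years, with round categorical, at least one cell is expected to be empty in about 66% (full follow-up) to 78% (80% retention) of trials. This rises to 84% to 91% under an assumed halving. Across 3 to 8 per 100 person-years, with equal rates and full follow-up, it runs from 92% down to 44%. Separately, and at any incidence, the interaction measures change in effect between rounds and not the intervention effect. The pooled ratio survives more often, but an empty arm is common enough that a Wald interval is unsafe.

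Severity: should be fixed. The arithmetic is firm; its inputs are assumptions to the extent stated.

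**What to change.** In SAP 6.2 and protocol 2.4.2, take HIV incidence out of the interaction GEE and state instead:

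- Infections, person-years and the rate per arm over the full 12 months, with exact Poisson 95% confidence intervals.
- One overall rate ratio with a conditional exact (mid-P) 95% confidence interval and no time or interaction term. This also settles how the SAP's person-time rate ratio is obtained.
- That the comparison is descriptive, because it remains very imprecise. The approximate power to detect a halving is only about 9% to 10%.
- What is reported if neither arm has an infection, when no ratio exists. The probability is e^−5.8 = 0.3% (equal rates, full follow-up) to e^−3.48 = 3.1% (halved incidence, 80% retention).

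Illustrative mid-P intervals with equal person-time: 1 infection under STOS versus 3 under control gives 0.33 (0.013 to 3.1); 0 versus 3 gives 0 (0 to 1.7). Both are wide, but they are usable intervals even with an empty arm.

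The cost is a few sentences in each document and a standard exact-rate analysis. Round-specific rate ratios are given up, and most of them would be unestimable or uninformative. The change makes the reporting honest; it does not add power.

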### 6.3 Multiple Comparisons and p-value Adjustment

For secondary outcomes and subgroup analyses involving several statistical tests, adjustments for multiple comparisons will be applied as appropriate. Methods such as Bonferroni correction or false discovery rate (FDR) procedures will be considered to control the risk of type I error.

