#### 2.4.3 Multiple Comparisons and p-value Adjustment

When multiple comparisons are made, such as in subgroup analyses or secondary outcomes, adjustments to p-values will be considered to control for the risk of type I error. Methods such as Bonferroni correction or false discovery rate (FDR) adjustment will be applied as appropriate.

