#### 3.3 Primary Outcome

- **HIV testing uptake:**

Proportion of participants who report having tested for HIV at least once within a 6-month period, based on STOS testing records and self-reported survey data.

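### Where the plan names plain Bonferroni for the secondary outcomes, Holm's step-down gives the same family-wise guarantee and never rejects less

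*Combined protocol and SAP*

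**What the plan says.** SAP 6.3 sets the scope: "For secondary outcomes and subgroup analyses involving several statistical tests, adjustments for multiple comparisons will be applied as appropriate". It then gives the tools: "Methods such as Bonferroni correction or false discovery rate (FDR) procedures will be considered to control the risk of type I error". Protocol 2.4.3 states the same purpose and the same tools: "Methods such as Bonferroni correction or false discovery rate (FDR) adjustment will be applied as appropriate".

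Neither section says which error rate is meant, at what level, or which tests form the family. Holm's procedure is not named, but the list is open and does not exclude it.

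SAP 3.4 has three secondary headings: HIV incidence ("Number of new HIV infections per 100 person-years"), sexual risk ("Proportion of participants reporting condomless anal intercourse with male partners during the past 6 months"), and a combined heading for mental health and substance use. Protocol 2.4.2 places one of these elsewhere: "The primary outcomes are the rate of HIV testing uptake and the rate of new HIV infections during the study period". SAP 6.2 adds that "rate ratios with 95% confidence intervals will be reported"; no significance level is stated.

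**The concern.** Plain Bonferroni tests each of m outcomes at 0.05/m. Holm starts at the same level for the smallest p-value and relaxes it after each rejection. Both hold the chance of any false positive at or below 5%, whatever the correlation between outcomes, so plain Bonferroni gives up power and gets no better error control in return. In a pilot with 50 men per arm, a real effect on a secondary outcome could be missed for no reason other than the choice of procedure.

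There is also a point of wording. Bonferroni bounds the chance of any false positive. An FDR procedure bounds the expected share of rejections that are false. Offering both for one purpose leaves the reader unable to tell what an adjusted p-value will mean.

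**Working it through.** **Inputs from the documents.** 100 men, 50 per arm (protocol 2); retention expected above 80% (protocol 2.1.3), so about 0.80 × 50 = 40 to 50 per arm at follow-up; outcomes as in SAP 3.4. The plan has no figure of its own to reproduce.

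**Assumptions.** Two-sided 5% level, taken from the 95% intervals. Family of m = 4: HIV incidence, condomless anal intercourse, mental health, substance use. Correlation 0.3 between test statistics. Power of each test alone: 30%, 45%, 50% or 80%.

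**Thresholds, m = 4.** Bonferroni: 0.05/4 = 0.0125 for every outcome. Holm, from smallest p-value to largest, stopping at the first failure: 0.05/4 = 0.0125, 0.05/3 = 0.0167, 0.05/2 = 0.025, 0.05/1 = 0.05. No Holm threshold is below 0.0125, so anything that Bonferroni rejects, Holm rejects too. This does not depend on the assumed power.

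**Bonferroni power by formula.** If a test has 50% power at 0.05, its mean z-statistic is about 1.96. The two-sided critical value at 0.0125 is 2.498. Power is Φ(1.96 − 2.498) = Φ(−0.538) = 29.5%. The same step gives 14.4% from 30% power, 25.4% from 45% and 61.9% from 80%.

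**Average power per real effect** (simulation, 200,000 replicates):

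| Power of each test alone | Real effects (of 4) | Bonferroni | Holm | Gain (points) |
|---|---|---|---|---|
| 30% | 1 | 14.4% | 14.5% | 0.1 |
| 30% | 4 | 14.4% | 16.5% | 2.1 |
| 45% | 1 | 25.4% | 25.5% | 0.1 |
| 45% | 3 | 25.4% | 27.9% | 2.5 |
| 50% | 2 | 29.6% | 30.9% | 1.3 |
| 50% | 4 | 29.6% | 34.9% | 5.3 |
| 80% | 2 | 62.1% | 64.4% | 2.3 |
| 80% | 3 | 61.9% | 67.3% | 5.4 |
| 80% | 4 | 61.9% | 71.6% | 9.7 |

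Holm's simulated family-wise error stayed below 5% in these settings.

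**Which row is plausible?** Take 50% v 30% on a binary outcome as an illustration. With 50 per arm, the standard error is √(2 × 0.4 × 0.6/50) = 0.0980 under the null and √((0.25 + 0.21)/50) = 0.0959 under the alternative. Power is Φ((0.20 − 1.96 × 0.0980)/0.0959) = 53%. With 40 per arm it is 45%. For HIV incidence, if the 5.8% cited for Hanoi in protocol 1.1 applied here, 50 men followed for a year would give 0.058 × 50 = 2.9 infections per arm. Even 0 v 3 of 50 gives a Fisher p-value of 0.24.

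**The FDR option, same settings.** With 45% power and three real effects, Benjamini-Hochberg at 5% has average power of about 32%, against about 28% for Holm. Its family-wise error there is below 3%; with one real effect it is about 5%. At 80% power with two real effects it is 5.9%. In a family of ten with five real effects it is 9.5%.

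**The case against.** The strongest reply is that the plan commits to nothing. The methods are examples, and Holm could be used under the present wording. A loss against plain Bonferroni is therefore a loss against one option, not against a fixed plan. That stands, and it limits the point to an improvement of a named option.

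A second reply is that Holm's gain is small at realistic power. That also stands: the table shows 0 to about 5 points at 30% to 50% power. The largest gains need four real effects, each with 80% power, and HIV incidence alone makes that implausible in this trial.

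A third reply is that Bonferroni has simple matching simultaneous intervals (1 − 0.0125 = 98.75% each for four outcomes), which Holm lacks. That is true, but the plan reports ordinary 95% intervals and does not use this advantage.

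A reader might go further and infer that, by stating type I error control as the purpose, the plan has already chosen family-wise control, so that naming FDR is a mistake. The documents do not support this. Neither section mentions family-wise error, and FDR stands in the same sentence as Bonferroni, so the term is being used loosely. Nor is dropping FDR free: Benjamini-Hochberg has more power than Holm, and at 45% power its family-wise error is about 5% or less.

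**Conclusion.** The point holds as a minor, nearly costless improvement. That Holm never rejects less than Bonferroni at the same family-wise bound is a mathematical fact. The size of the gain is not: for four outcomes at correlation 0.3 it is about 0 to 2 points of average power at 30% single-test power, 0 to 5 at 50% and 0 to 10 at 80%, rising with the number of real effects. Family size, correlation, level and single-test power are all assumed. Bonferroni would be valid, only less efficient, and FDR is a legitimate alternative if it is labelled as what it is. The primary outcome in SAP 3.3 lies outside the adjustment and is not affected.

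**What to change.** First reconcile protocol 2.4.2, where new HIV infections are primary, with SAP 3.4, where they are secondary. This decides the family: on the count used here it has four members, or three if infections are primary. State at the same time whether mental health and substance use count as one, two or more outcomes.

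Then, in SAP 6.3 and protocol 2.4.3, replace the Bonferroni option with: *Holm's step-down procedure at a two-sided 5% level, applied to the secondary outcomes in SAP 3.4, with one pre-named arm contrast per outcome.* The contrast must be named because the arm-by-time model in SAP 6.2 can yield more than one arm comparison per outcome. Both sections also cover subgroup analyses but list none; either list them or report them as exploratory, outside the family.

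If the sponsor prefers FDR for these pilot outcomes, name the procedure and its level, and describe it as control of the false discovery rate, not of family-wise type I error.

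The cost is about a sentence in each document. The drawback is that Holm has no simple matching simultaneous intervals, so the planned unadjusted 95% intervals would stand beside adjusted p-values and may occasionally seem to disagree with them. A footnote to the results table can say so.
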